6.6 Prohibited Medications

No medications are prohibited during this brief trial. For those wearing hearing aids at the time of the trial, they are asked to refrain from use of their personal hearing aids during the course of this study and while using the Jabra Enhance Plus devices.

7.0 TRAINING PLAN

7.1 Training Plan for Research Device

All relevant study site personnel and participating subjects will be trained on the investigational device using standardized training materials. All study site personnel will be trained before research begins.

7.2 Training Plan for Protocol

All study site personnel will be trained on the study protocol using standardized training materials. All study site personnel will be trained before research begins.

8.0 DATA ANALYSIS AND STATISTICS

8.1 Statistical Analysis Methods

8.1.1 In-Lab – *Test-Retest Reliability* (initial Self-Fit A vs. initial Self-Fit B)

- i. Paired-sample t-tests of equivalence of the four-frequency (500, 1000, 2000 and 4000 Hz) average REAG and the QuickSIN comparing initial-fit settings from the SELF-FIT A procedure and the initial-fit settings from the SELF-FIT B procedure.
- ii. Supplementary analyses will include examination of the distribution of differences in dB between the four-frequency average REAGs and the QuickSIN threshold SNRs for initial-fit settings from the SELF-FIT A and B procedures, as well as computation of test-retest correlation coefficients for each measure.

8.1.2 In-Lab *REAG – Validity* (initial Pro-Fit vs initial Self-Fit A)

- i. Paired-sample t-test for equivalence of the means of the initial-fit settings of the SELF-FIT A procedure to the means of the initial-fit settings of the PRO-FIT procedure
- ii. Supplementary analyses will include examination of the distribution of differences in dB between the four-frequency average REAGs for initial-fit settings of the SELF-FIT A procedure and initial-fit settings of the PRO-FIT procedure, as well as computation of correlation coefficients between the two measures.

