3.0 OBJECTIVES OF RESEARCH STUDY

3.1 Hypotheses

3.1.1 In-lab validation component-Primary

- Null hypothesis: Mean $|REAG_{PRO-FIT} - REAG_{SELF-FIT}| \geq 2.5$ dB
- Alternative hypothesis: Mean $|REAG_{PRO-FIT} - REAG_{SELF-FIT}| < 2.5$ dB

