3.1.2 In-lab validation component-Secondary

- Null hypothesis: Mean $|QuickSIN_{PRO-FIT} - QuickSIN_{SELF-FIT}| \geq 1.5$ dB
- Alternative hypothesis: Mean $|QuickSIN_{PRO-FIT} - QuickSIN_{SELF-FIT}| < 1.5$ dB

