3.1.4 Wear-Time Field Trial-Secondary

- Null hypothesis: Mean difference $(QuickSIN_{PRO-FIT} - QuickSIN_{SELF-FIT}) \geq 1.5$ dB
- Alternative hypothesis: Mean difference $(QuickSIN_{PRO-FIT} - QuickSIN_{SELF-FIT}) < 1.5$ dB

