3.1.5 In-Lab Session-Reliability Component-Primary

- Null hypothesis: Mean $|REAG_{SELF-FIT A} - REAG_{SELF-FIT B}| \geq 2.5$ dB
- Alternative hypothesis: Mean $|REAG_{SELF-FIT A} - REAG_{SELF-FIT B}| < 2.5$ dB

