3.1.6 In-Lab Session-Reliability Component-Secondary

- Null hypothesis: Mean difference $|QuickSIN_{SELF-FIT A} - QuickSIN_{SELF-FIT B}| \geq 1.5$ dB
- Alternative hypothesis: Mean difference $|QuickSIN_{SELF-FIT A} - QuickSIN_{SELF-FIT B}| < 1.5$ dB

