3.2 Study Endpoints

3.2.1 Primary Effectiveness Endpoint(s)

For the validation component of the immediate in-lab session comparisons, Real-Ear Aided Gain (REAG) will be measured using both an audiology-best-practices (professional) hearing aid fitting (PRO-FIT) and a self-fitting method (SELF-FIT).

- Success criterion is defined as SELF-FIT REAG is equivalent to PRO-FIT NAL-NL2 prescription REAG targets based on the average real-ear aided gain at 500, 1000, 2000 and 4000 Hz.

For the reliability component of the immediate in-lab session comparisons, Real-Ear Aided Gain (REAG) will be measured twice (A, B) using the SELF-FIT method.

- Success criterion is four-frequency average REAG for SELF-FIT B is equivalent to the REAG for SELF-FIT A based on the average real-ear aided gain at 500, 1000, 2000 and 4000 Hz.

For the wear-time crossover field trial, the APHAB will be measured following both an audiology best-practices hearing aid fitting (PRO-FIT) and a self-fitting method (SELF-FIT).

- Success criterion is defined as SELF-FIT APHAB global score is non-inferior to PRO-FIT APHAB global scores following completion of the wear-time field trial.

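### The two primary in-lab REAG hypotheses are written on the mean absolute difference, but the only planned tests address the signed mean difference

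*Combined protocol and SAP*

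**What the plan says.** **Hypotheses.** For REAG validity, section 3.1.1 gives "Alternative hypothesis: Mean $|REAG_{PRO-FIT} - REAG_{SELF-FIT}| < 2.5$ dB". For REAG reliability, section 3.1.5 gives "Alternative hypothesis: Mean $|REAG_{SELF-FIT A} - REAG_{SELF-FIT B}| < 2.5$ dB". In both, the absolute value stands inside the mean. The in-lab QuickSIN secondaries carry the same bars with a 1.5 dB margin: "Alternative hypothesis: Mean $|QuickSIN_{PRO-FIT} - QuickSIN_{SELF-FIT}| < 1.5$ dB" in 3.1.2 and, more loosely, "Alternative hypothesis: Mean difference $|QuickSIN_{SELF-FIT A} - QuickSIN_{SELF-FIT B}| < 1.5$ dB" in 3.1.6. The field-trial QuickSIN hypothesis in 3.1.4 has no bars: "Alternative hypothesis: Mean difference $(QuickSIN_{PRO-FIT} - QuickSIN_{SELF-FIT}) < 1.5$ dB".

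**Words.** Sections 1.5.3.1 and 8.4 contain the same paragraph. It says that the REAG endpoint serves to assess average absolute differences, both between the two self-fits and between self-fit and professional fit. The synopsis (Statistical Considerations) says that mean absolute differences will be reported by visit, and attaches no test to them.

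**Success criteria.** Section 3.2.1 and the synopsis speak only of equivalence: "SELF-FIT REAG is equivalent to PRO-FIT NAL-NL2 prescription REAG targets" and "four-frequency average REAG for SELF-FIT B is equivalent to the REAG for SELF-FIT A". Either quantity fits that wording.

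**Tests.** Section 8.1.1 plans paired t-tests of equivalence for reliability (REAG and QuickSIN). Section 8.1.2 plans a "Paired-sample t-test for equivalence of the means of the initial-fit settings of the SELF-FIT A procedure" against PRO-FIT, and 8.1.3 does the same for QuickSIN. The other items there are descriptive (distributions of differences, correlations). Section 8.1 states neither a margin nor a significance level.

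**The concern.** A paired equivalence t-test asks whether the average of the signed differences lies within the margin. The written hypothesis asks whether the average size of the differences is below the margin. The absolute mean can never exceed the mean absolute value, so the second requirement is the stricter one.

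Take 18 subjects at +4 dB and 18 at −4 dB. The mean difference is 0 and the mean absolute difference is 4 dB, so the written null is true. The SD is 4 × √(36/35) = 4.06 dB, and the 90% confidence interval is 0 ± 1.69 × 4.06/√36 = ±1.14 dB. The planned test passes comfortably.

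Section 8.4 makes overall success depend on every primary endpoint, and two of the three primary effectiveness endpoints are affected. The results are meant to support a 510(k) submission (sections 2.5 and 15.0). Section 13.1 also lets Visit 1 results go to the sponsor before the study ends, so an unresolved choice between the two quantities could end up being made with the data in view.

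**Working it through.** **The plan's own figures.** The synopsis claims about 80% power at 0.05 for the in-lab comparisons but gives no in-lab SD, so that figure cannot be reproduced. The only sizing with complete inputs is for APHAB (section 5.1: SD of differences 0.163, margin 0.084, 2.5% level, true difference 0). It does reproduce: N = 32 gives 80.5% power by the noncentral t. It is not in dispute.

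**Inputs**
- n = 36 (synopsis, 5.1).
- Margins of 2.5 dB for REAG and 1.5 dB for QuickSIN (3.1). Using them as ± margins in the signed test is an inference.
- One-sided 5%, inferred from the 0.05 in the synopsis.
- Differences d normal with mean 0 and standard deviation SD. The SD is an assumption throughout.

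**Where the written null becomes true.** At zero bias, E|d| = SD × √(2/π) = 0.798 × SD. Setting this equal to the margin:
- REAG: 2.5/0.798 gives SD = 3.13 dB.
- QuickSIN: 1.5/0.798 gives SD = 1.88 dB.

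**Hand check at the REAG boundary.** The standard error is 3.13/6 = 0.522. The 90% half-width is 1.69 × 0.522 = 0.88. The signed test passes if the observed mean lies within 2.5 − 0.88 = 1.62 dB, which is 3.1 standard errors, so it passes almost always.

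**Simulation** (200,000 trials per row). Signed test: the 90% CI of mean d lies inside ±2.5. t bound: mean|d| + t(0.95, 35) × sd(|d|)/√36 < 2.5.

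| SD (dB) | E\|d\| (dB) | Written null | Signed test passes | t bound on mean \|d\| passes |
|---|---|---|---|---|
| 2.0 | 1.60 | false | 100% | 99% |
| 2.3 | 1.84 | false | 100% | 85% |
| 2.55 | 2.03 | false | 100% | 56% |
| 3.13 | 2.50 | boundary | 99.8% | 7.0% |
| 3.5 | 2.79 | true | 99% | 1.2% |
| 4.0 | 3.19 | true | 96% | 0.1% |

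- **Significance level.** At 2.5% per side the boundary row becomes 99.3% and 4.2%, so the inferred level does not drive the result.
- **Bias.** With a bias of 1 dB the boundary SD is 2.97 dB and the signed test passes 91% of the time there. With 2 dB (boundary 2.32 dB) it passes 35%.
- **Skewness.** The plain t bound slightly exceeds its nominal 5% (7.0%) because |d| is skewed. A studentized bootstrap bound gives 4.9%.
- **QuickSIN.** At its boundary SD of 1.88 dB the rates are again 99.8% and 7%.

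**Which SD might apply.** The only guide is the data-quality check in section 13.1. It expects test-retest differences generally under 5 dB at a given frequency, and PRO-FIT within 5–7 dB of target. Reading these as 95% limits is an assumption. Let r be the correlation between frequencies.
- *Reliability:* SD = (5/1.96) × √((1+3r)/4) = 1.28, 2.02 and 2.55 dB for r = 0, 0.5 and 1. All lie below 3.13.
- *Validity:* assume also that SELF-FIT strays from target as far as PRO-FIT does, with correlation c between the two fits. Then SD = (q/1.96) × √(2(1−c)) × √((1+3r)/4). With c = 0 this runs from 1.80 dB (q = 5, r = 0) to 5.05 dB (q = 7, r = 1). With c = 0.5 it runs from 1.28 to 3.57 dB. For c = 0.5 and q = 7 it reaches 3.13 dB when 3.57 × √((1+3r)/4) = 3.13, that is, at r of about 0.69.
- Any averaging over the two ears would lower these SDs. The plan does not say whether ears are averaged.

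**SD that gives 80% power at n = 36 (REAG).** About 2.35 dB for the t bound on mean |d|, and about 5.0 dB for the signed test. An SD of 5.0 dB corresponds to a mean |d| of about 4.0 dB, well inside the written null.

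**The case against.** The strongest reply is that the bars are loose notation. They appear exactly where an equivalence test is planned (3.1.1, 3.1.2, 3.1.5 and 3.1.6, against 8.1.1 to 8.1.3) and are absent exactly where a non-inferiority test is planned (3.1.3 and 3.1.4, against 8.1.4 and 8.1.5). Equivalence is commonly written as |mean difference| below a margin, and 3.1.6 comes close to that form. The success criteria speak only of equivalence, and the synopsis sets the hypothesis test apart from the mean absolute values, which it merely reports.

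Much of this stands. The contrast between 3.1.2 and 3.1.4 does not show that the bars were deliberate. For QuickSIN nothing outside 3.1 mentions absolute values, so those secondaries are only supporting evidence. For REAG the reply falls short: 1.5.3.1 and 8.4 describe the absolute value in words as taken before averaging. That is one repeated paragraph and counts once, but it sits in the pass/fail section. If loose notation is the explanation, 3.1, 1.5.3.1 and 8.4 are the parts that need correcting, so the sections conflict on either reading.

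The second reply is that practical impact is unproven. That is right as far as it goes. With no in-lab SD, the validity range rests on several stacked assumptions.

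**Conclusion.** The conflict is real and concerns a primary decision rule. For REAG, the hypotheses and the pass/fail section state one quantity and the analysis section tests another, so a pass on the planned test would not establish what sections 3.1 and 8.4 say is to be shown.

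The size is conditional on the unstated SD, on normal differences without bias, and on the inferred margin and level. Up to about 2 dB the two criteria agree. From there to 3.13 dB the written null is false and they differ in power (100% against 56% at 2.55 dB). From 3.13 dB upward a pass on the signed test is wrong, and it would occur 99.8% of the time at the boundary and 96% at 4.0 dB.

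A reader might infer that the trial is likely to declare a false success. The documents do not support that. On the section 13.1 checks, read as 95% limits, reliability probably lies below the boundary, so a pass there would probably be correct; validity may lie on either side. A reader might also infer that the sponsor certainly intended absolute differences, or that the QuickSIN case is equally firm. Neither is established.

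**What to change.** Before any Visit 1 result is shared with the sponsor, choose one quantity and use it in 3.1, 3.2.1, 8.1, 8.4 and the synopsis, with the margin and significance level stated in 8.1.

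**(a) Mean absolute difference.** Average REAG over the four frequencies for each subject, and state whether ears are averaged before the absolute value is taken. Declare success if the one-sided 95% upper bound of mean |d| is below 2.5 dB (1.5 dB for QuickSIN). Name one method for the bound that suits skewed data, such as a studentized bootstrap. Report the signed mean with its 90% CI as support.

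**(b) Signed equivalence.** Rewrite 3.1.1, 3.1.2, 3.1.5, 3.1.6, 1.5.3.1 and 8.4 as |mean difference| below the margin, tested by two one-sided tests at 5%. Report mean |d| with its CI descriptively, and do not claim that a mean absolute deviation below 2.5 dB was shown.

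Under either option, restate the synopsis power for the REAG tests as conditional on a stated SD of differences: about 2.35 dB or less under (a) with a t bound, somewhat lower with a bootstrap bound, and about 5.0 dB or less under (b).

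**Cost.** Wording and a small change of code, with no new data. Option (a) is stricter and loses power at larger SDs: at 2.55 dB it has 56% power with the t bound and 49% with the bootstrap bound. Option (b) keeps the power but supports a weaker conclusion, because individual errors in opposite directions can still cancel.

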Primary Safety Objectives/Endpoints:	
Tabulations of Adverse Events (AEs) and Serious Adverse Events (SAEs).
 
○ Success criterion is no recorded device-related AEs or SAEs.
Inclusion Criteria:	
An initial telephone or internet screening of interested persons will take place.
 
• During this remote screening, prospective subjects will provide their age (subject to verification at Visit 1) and answer a Yes/No question as to whether they have trouble hearing in noise. Those answering "No" will not be considered further for enrollment.• Those answering "Yes" will then be asked to describe their perceived hearing loss on a 4-point scale (no trouble, a little trouble, a lot of trouble, and cannot hear). Prospects answering at the two extremes will not be considered further for this study.• Those answering "a little trouble" or "a lot of trouble" will be invited to the in-person Screen that immediately precedes hearing aid fittings in Visit 1. To be eligible to participate in this study, an individual must meet all of the following criteria:

	
 • Mild-to-moderate bilateral sensorineural hearing loss (thresholds from 250 – 8000 Hz with at least one threshold greater than 20 dB HL and thresholds at 500, 1000, 2000 and 4000 Hz less than or equal to 55, 65, 70, and 80 dB HL, respectively) • Mix of male and female subjects (aiming for a representative balance) • Mix of prior hearing-aid use (aiming for 70-80% persons with no prior hearing aid use) • 18-75 years old (aiming for primarily 50-70 years old, with avg. age ~65 years) • Able to read and comprehend English • Patient willing to provide informed consent
Exclusion Criteria:	
An individual who meets any of the following criteria will be excluded from participation in this study:
 
 • Hearing outside of limits noted above • Self-reported ear-related pathology (including chronic severe dizziness or chronic severe tinnitus)
Sampling Frame:	
The proposed sample size of n=36 subjects will be sufficient to rule out a null hypothesis of non-equivalence of SELF-FITs A and B (reliability) or SELF-FIT A and PRO-FIT (validity) with about 80% power with 0.05 significance level. In addition, distributions of deviations from the standard-of-care measures will be generated for the primary and secondary measure and for the reliability and validity components of the study.

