5.0 STUDY SUBJECTS

5.1 Sample Size Determination

The sample size was powered by the primary outcome measure of the wear-time field trial, the APHAB, as it is the most variable of the outcome measures across all components of this study. When the sample size in each sequence group in the crossover trial is 16 (giving a total sample size of 32), a crossover design will have 80% power to reject the null hypothesis that the SELF-FIT APHAB mean is inferior to the PRO-FIT APHAB mean based on the mean difference, in favor of the alternative hypothesis that the SELF-FIT mean is non-inferior to the PRO-FIT mean, assuming that the expected difference in means is 0, the non-inferiority difference margin is .084 (or 8.4%), the Crossover ANOVA \sqrt{MSE} is 0.115 (or 11.5%) (giving a standard deviation of differences, σ , of 0.163 or 16.3%) and that the test is made at the 2.5% significance level.

The overall design for the in-lab session is a repeated-measures design comparing outcomes for three procedures: SELF-FIT A, SELF-FIT B, PRO-FIT. Given that SELF-FIT A and B are the same procedure repeated two times, this results in three possible procedure sequences: (1) SELF-FIT A, SELF-FIT B, PRO-FIT; (2) SELF-FIT A, PRO-FIT, SELF-FIT B; and (3) PRO-FIT, SELF-FIT A, SELF-FIT B. An equal number of subjects will receive each sequence at each site to ensure full counterbalancing of order. A total of 36 subjects, 18 per site, will be included which meets the minimum of 32 required for sufficient statistical power, achieves the desired counterbalancing, and allows for some subject attrition or missing data.

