6.2 Study Procedures

6.2.1 Pre-Fitting Procedures: After consent, otoscopy, and audiological measurements verifying candidacy for the study, the subject completes Pre-Fitting of the devices. If the subject does not have a compatible iPhone running iOS 14, one will be supplied for use in this study. The investigator will install the app on the subject's smartphone, pair the devices to the smartphone, and select the appropriate earbud size for each ear prior to the PRO-FIT and SELF-FIT procedures. (These aspects of the fitting process for the Jabra Enhance Plus will be evaluated separately in a usability study.)

i. Fitting begins by placing probe-tube microphones in the subject's ear canals and measuring the Real-Ear Unaided Response (REUR) for each ear.

ii. The Jabra Enhance Plus, powered off, will be placed in the subject's ear with medium-sized earbuds and the Real-Ear Occluded Response (REOR) measured.

- If measurable passive attenuation at frequencies above 500 Hz is not seen, a smaller or larger earbud will be selected by the audiologist and REOR will be remeasured.
- This process will be repeated as needed until a good seal is obtained as verified by the REOR.
- The selected earbud size for each ear will be used by the subject during the remainder of the study.

6.2.2 PRO-FIT: The audiologist will use the air-conduction thresholds measured during the initial screening to generate REAR targets for the NAL-NL2 prescriptive procedure.

- i. Targets will be generated for a speech input level of 65 dB SPL.
- ii. Fine-tuning of REAR by the audiologist to match NAL-NL2 targets will be accomplished using custom device-programming software (AlgoLabTest) to program the gain and compression parameters for NAL-NL2.
- iii. The Audioscan Verifit 1 or 2 real-ear measurement system will be used to verify and fine-tune the fit to match targets for this initial fit for speech input level of 65-dB SPL.

- iv. If the subject has immediate sound-quality complaints, the audiologist will fine-tune the fitting to accommodate those complaints (as was done for the predicate device study; Sabin *et al.*, 2020). The range of adjustments to the frequency response will be constrained to the two alternative responses available on the device via the app. This will be the final fit for PRO-FIT to be worn during the wear-time trial.

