- v. The SELF-FIT process continues uninterrupted with user-preferred adjustments of "filters" or frequency-gain responses. These user-driven fine-tuning adjustments are made while streaming a sound file to the devices and comparing filter settings. (See Attachment 4A for details.) When the subject selects the final settings, these

device settings are saved and become the new default settings for when the device is powered on. These settings are referred to as the "final fit" for the SELF-FIT procedure. Measurements made for SELF-FIT A and PRO-FIT at the end of each wear-time crossover field trial will make use of these *final-fit* settings.

- vi. Once the subject has completed the test, the app will indicate that the subject is finished with personalization of the devices and will return to the home screen of the app.

6.2.4 SELF-FIT B: To assess test-retest reliability, subjects will complete the self-fitting procedure a second time (repeat steps for SELF-FIT A above).

6.2.5 Overview of Procedures at Visits 1, 2, and 3

Successive subjects will be assigned to one of these six condition sequences illustrated in Figure 1 with a total of two cycles through the full set of six sequences at each of the three sites. In the end, two subjects will have been tested in each of the six sequences at each site, six per sequence for the entire study, and any effects of order will be equalized across conditions following the counterbalancing illustrated in Figure 1.

The table below summarizes the primary and secondary outcome assessments to be completed during each study visit. For Visits 2 and 3, REAG will also be established but only for potential explanatory purposes and not as an outcome measure.

Visit	Primary Outcome	Secondary Outcome
1	REAG from REAR; initial fit	QuickSIN; initial fit
2	APHAB; final fit	QuickSIN; final fit
3	APHAB; final fit	QuickSIN; final fit

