8.1.4 Wear-Time Field Trial - *Validity: APHAB* (final PRO-FIT vs. final SELF-FIT A)

- i. Non-Inferiority t-Test for 2 (wear-time sequences) X 2 (fit conditions)
- ii. Supplementary analyses will include examination of the distribution of differences between the APHAB-global scores for final-fit settings of the SELF-FIT A procedure and final-fit settings of the PRO-FIT procedure, as well as computation of correlation coefficients between the two measures. Datalogging will also provide details of the subject's adjustment of the devices during each segment of the cross-over wear-time trial.

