13.1 Management of Data

High data quality standards will be maintained, and processes and procedures utilized to repeatedly ensure that the data are as clean and accurate as possible when presented for analysis. Data quality will be enhanced through a series of programmed data quality checks that automatically detect out of range or anomalous data.

The following practices are adopted to ensure data integrity and participant safety:

1. Data, including outcomes data, should not be shared with GN Hearing A/S until study completion. There are two components to this study: (1) in-lab session (Visit 1); and wear-time crossover trial (Visits 2 and 3). Outcome data can be shared with GN Hearing A/S at the completion of each component to this study. That is, the results from Visit 1 can be shared with the sponsor as soon as they are available and prior to the completion of the entire study.
2. The site investigators should be blinded from the raw data and the research staff on site should enter the data into an electronic database (REDCap). Weekly reports of completed data for each visit will be generated by research staff at each site and will be sent to [name]. Progress reports, generated by [name], will tabulate the number of subjects who have complete data for Visit 1, Visit 2, and Visit 3, for each site separately and combined. Such progress reports will be provided via email to GN Hearing A/S ([name] and [name]) and shared with the site investigators ([name], [name]) on a weekly basis.
3. [name] will monitor the quality of the data exported from REDCap. PRO-FIT REAG values will be checked to determine that they are reasonable, within 5-7 dB of NAL targets, for the measured pure-tone hearing loss for that participant. The pattern across frequency for the REAG differences between test and retest will also be examined to assess data validity. Such differences should generally be less than 5 dB at a given frequency and also should not decrease with increasing frequency. Concerns about the quality of data being gathered will be shared with each site investigator and GN Hearing A/S as soon as possible.

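### The SELF-FIT versus PRO-FIT tests leave out site, although allocation is balanced within site and only PRO-FIT is tuned by an audiologist

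*Combined protocol and SAP*

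**What the plan says.** **Allocation.** Section 6.2.5 runs two cycles of six sequences at each of three sites, so that "two subjects will have been tested in each of the six sequences at each site". That is 12 per site and 36 in total.

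**Analysis.** Section 8.1.2 plans a "Paired-sample t-test for equivalence of the means of the initial-fit settings of the SELF-FIT A procedure" against PRO-FIT, and 8.1.3 does the same for in-lab QuickSIN. Sections 8.1.4 (APHAB) and 8.1.5 (field QuickSIN) plan a "Non-Inferiority t-Test for 2 (wear-time sequences) X 2 (fit conditions"). None of these names site, a site-by-fit comparison or a rule for pooling sites.

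**How the two fits arise.** In 6.2.3 and 6.2.6 the device produces the initial SELF-FIT from the subject's own responses. In 6.2.2, PRO-FIT involves "Fine-tuning of REAR by the audiologist to match NAL-NL2 targets", and Attachment B asks the operator to try to match the target curve. Section 13.1 adds a central check: "PRO-FIT REAG values will be checked to determine that they are reasonable, within 5-7 dB of NAL targets".

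**Hypothesis.** Section 3.1.1 sets the 2.5 dB margin on the mean absolute REAG difference, whereas 8.1.2 tests equivalence of means.

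**The concern.** A within-subject difference cancels a site effect only when both fits share it, as with booth acoustics or case mix. An offset that comes from how PRO-FIT is tuned belongs to one fit only and stays in the difference. Two consequences follow if site is left out.

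- Between-site variation in the contrast is counted as residual error, so the interval is wider than it need be.
- If sites lean in opposite directions, a signed mean can sit near zero while individual sites do not. The planned test would not distinguish this from agreement at every site.

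In-lab REAG and field APHAB are both primary, and section 8.4 requires every primary endpoint to be met. The design already balances on site, so using that factor in the analysis is the natural counterpart.

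**Working it through.** **1. The plan's own figure.** Section 5.1 gives an APHAB margin of 0.084, an SD of differences of 0.163 (√2 × 0.115 = 0.1626) and an expected difference of 0. It states "that the test is made at the 2.5% significance level" and that "a crossover design will have 80% power to reject the null hypothesis" with 32 subjects. Noncentral t with N − 2 df and noncentrality 0.084/(0.163/√N):

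- N = 32: noncentrality 2.915, 30 df, power 80.5%. The stated figure reproduces.
- N = 36: noncentrality 3.092, 34 df, power 85.2%.
- N = 36 with site added and no true site differences: 32 df, power 85.0%.

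**2. Error-term inflation, formula.** With 12 per site and fixed offsets (−d, 0, +d), the between-site sum of squares is 12 × 2d² = 24d². The pooled SD therefore grows by √(1 + 24d²/(df × SD²)), with 35 df for the paired test and 34 df for the crossover test.

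**3. REAG.** The documents give no SD and no offsets. Assumed: within-site SD 2.5 dB and two one-sided tests at 5% each. The synopsis says "with about 80% power with 0.05 significance level" but not whether that is per side.

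- No offsets: half-width ≈ 1.690 × 2.5/6 = 0.70 dB pooled. With site (33 df) it is 1.692 × 2.5/6, again 0.70 dB to rounding.
- Offsets ±2 dB: inflation √(1 + 96/218.75) = 1.20, so the pooled half-width is about 0.84 dB (simulated mean) against 0.70 dB with site.
- Power at a true mean of 0 is about 100% in every one of these cases, pooled or with site.
- A larger SD leaves more room for a loss. At SD 5 dB and offsets ±2.5 dB, the SD rises 8% and power at a mean of 0 is 75.9% pooled against 80.8% with site.

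**4. APHAB with site differences.** N = 36, within-site SD assumed to be 0.163, true mean 0:

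| Offset d | SD inflation | Pooled power | Power with site |
|---|---|---|---|
| 0 | 0% | 85.1% | 84.9% |
| 0.04 | 2.1% | 84.0% | 84.9% |
| 0.06 | 4.7% | 83.2% | 85.3% |
| 0.084 | 9.0% | 80.8% | 85.2% |

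These are simulated; in the first row the exact values are the 85.2% and 85.0% of step 1. Section 5.1 does not say whether 0.163 already contains site variation. If it does, pooled power is 85.2% throughout and a site term would raise it.

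**5. Averaging out, signed test of 8.1.2.** SD 2.5 dB, offsets +3.5/0/−3.5 dB, overall mean 0: the pooled test passes about 99.9% of the time with two of three sites outside ±2.5 dB. With a site term it passes about 100%. The term leaves the estimate unchanged (equal site sizes) and narrows the interval, so it does not reveal the pattern.

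What does reveal it is the set of site estimates and the test of the site factor. A site mean has a 90% half-width of about 1.2 dB (1.692 × 2.5/√12). The F-test of site at 5% detects ±2 dB about 93% of the time at SD 2.5 dB. For ±2.5 dB it detects 94.5% at SD 3 dB, 74% at SD 4 dB and 54% at SD 5 dB.

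**6. The same offsets under 3.1.1.** For a normal difference with mean μ and SD σ, the mean absolute value is σ√(2/π)·exp(−μ²/2σ²) + μ(1 − 2Φ(−μ/σ)). At σ = 2.5 this is 3.68 dB for μ = ±3.5 and 1.99 dB for μ = 0. The average is (2 × 3.68 + 1.99)/3 = 3.12 dB, above 2.5 dB, and the pass rate is close to zero. At SD 3 dB, offsets of ±2.5 dB move the pass rate from 12.6% to 0.4%. Here offsets add rather than cancel.

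**The case against.** **The hypothesis is on the absolute difference.** Sections 3.1.1, 1.5.3.1 and 8.4 speak of absolute differences, for which nothing averages out. This stands as a limit: averaging out applies only to the test of means in 8.1.2. The two sections conflict, and modelling the signed difference without saying so would settle that conflict silently.

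**Fitting is standardised.** There is a common NAL-NL2 target, real-ear verification, standard training, and complaint-driven changes limited to two alternative responses. Section 3.2.1 even words success against the prescription targets. All this should keep offsets small, and it is also an inference that each site has its own audiologist. It does not show that offsets are zero.

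**The 5–7 dB check.** A reader might take it as permission for a site to be off by two to three times the margin. The documents do not support that: it is a plausibility screen on individual participants, neither a fitting tolerance nor a bound on a site mean. It simply cannot be relied on to exclude a site offset.

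**Power.** A reader might infer a serious loss. With a true mean difference of 1.5 dB and SD 2.5 dB, pooled power falls to about 65% at offsets of ±2 dB and 43% at ±3.5 dB, against 76% with site. But a 1.5 dB difference appears nowhere in the documents; the one planning value, for APHAB, is 0. Leaving site out also makes the pooled test conservative, so false-positive control is not threatened.

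**Site patterns would not go wholly unseen.** Section 8.1.2 plans the distribution of differences, and 13.1 plans data reduction and analyses as each site finishes. Neither specifies a site comparison or what would be done with one.

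**Conclusion.** The concern holds in a limited form. The SELF-FIT versus PRO-FIT tests in 8.1.2 to 8.1.5 ignore a factor on which allocation is balanced, and pairing does not remove a site difference that enters through PRO-FIT alone. The effect on precision is modest: a REAG half-width of up to 0.84 against 0.70 dB under the assumed SD of 2.5 dB and offsets up to ±2 dB, with power near 100% at a mean of 0. APHAB power falls at most about 4 points, to 80.8%, with offsets as large as the whole margin.

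The stronger reading, that equivalence could be declared over sites lying outside the margin, depends on the signed test in 8.1.2 and on offsets that nothing in the documents establishes. It reverses under 3.1.1. Section 8.1.1 is not affected on this ground, because PRO-FIT plays no part there. The change is worth making because it is specific and nearly free, not because the trial is likely to fail without it.

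**What to change.** 1. Reconcile first. Decide whether the REAG criterion is the mean absolute difference (3.1.1) or equivalence of means (8.1.2). Reconcile the site counts too: 5.1 gives 18 per site and 6.2.5 has 9 starting on each fit per site, which over three sites makes 54 rather than 36, while the sequence scheme in 6.2.5 gives 12 per site. Section 13.1 still refers to two sites.
2. In 8.1.2 to 8.1.5, model the within-subject difference with site as a three-level fixed factor and equal site weights, adding wear-time sequence in the field trial. Take the equivalence or non-inferiority interval from that model. Margins and significance levels stay as they are. If the absolute criterion is kept for the in-lab tests, apply the site factor to that quantity.
3. Pre-specify, as supportive outputs, site-specific mean differences with confidence intervals and the test of the site factor. In a model of within-subject differences that test is the site-by-fit test. These outputs, not the site term, are what would show opposite offsets.

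The cost is 2 degrees of freedom (APHAB power 85.2% to 85.0% at N = 36 if sites do not differ) and one extra table. No new data are needed.
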